10.0 MEASURES TO AVOID & MINIMIZE BIAS

The study has several measures that have been implemented to avoid and minimize bias including:

- Use of an independent CRO for study operations management, monitoring, and data management.
- Establishment of a Clinical Events Committee to independently review and adjudicate adverse events.
- Use of an independent angiographic core laboratory for systematic review of images removing any potential for Investigator bias.

10.1 Clinical Events Committee

All adverse events will be arbitrated by the Clinical Events Committee (CEC). The CEC, which is made up of at least two interventional cardiologists who are not Investigators in the study, will adjudicate and classify adverse events for seriousness, and device and/or procedure relationship following written CEC Adjudication Guidelines. Sites will be expected to provide supporting de-identified source documentation as requested to assist CEC adjudication.

10.2 Angiographic Core Laboratory

An angiographic core laboratory will be used to provide an unbiased assessment of angiographic imaging. The angiographic core laboratory will provide image acquisition and processing instructions to the sites. The angiographic core laboratory will follow its own Charter or similar procedure to systematize their image review in compliance with the study protocol.

11.0 ADVERSE EVENTS

11.1 Adverse Event Definitions

Refer to **Section 14.0** for adverse event definitions.

The following are not considered adverse events for this study:

- Any condition that is recorded as pre-existing on the Baseline CRF, unless there is a worsening of that condition in terms of nature, severity, or degree of incidence.
- Any normal expected symptoms associated with PCI unless the event involves a clinically significant change in severity or duration of symptoms or requires clinical intervention that is different from ordinary postoperative care. The following are examples of the normal responses to all PCI procedures and are not considered AEs:
 - Transient arterial spasm resolving spontaneously OR with medication only
 - Transient sinus bradycardia with heart rate ≤ 50 bpm, with no hemodynamic impact, and resolving spontaneously (Prophylactic placement and automatic activation of a cardiac pacer during this transient period does not constitute an intervention)
 - Minor discomfort or bruise at the arterial access place
 - Small amount of bleeding at point of arterial access that does not result in a hematoma > 5 cm, need for transfusion, or hemodynamic compromise
 - Side effects of standard-of-care medications

11.2 Adverse Event Collection & Documentation

Collection of adverse events will start when subjects are enrolled and will be assessed and reported throughout the study. Investigators must obtain all information available to determine the causality and outcome of the adverse event and to assess whether it meets the criteria for classification as a related serious adverse event requiring immediate notification. All adverse events will be followed until resolution or Investigator determination that the subject's condition is stable.

All reported adverse events will be documented on the Adverse Event CRF. Copies of de-identified source documentation that contain significant information related to the event, such as progress notes, consultations, nurse's notes, operative reports and subject summaries, etc. may be requested by the Sponsor, CRO, CEC and/or angiographic core lab as needed for evaluation and adjudication.

Device deficiencies will also be collected. If a device deficiency results in the subject experiencing any untoward medical occurrence, unintended disease or injury, or untoward clinical signs, these outcomes will be reported as an adverse event on an Adverse Event CRF. Any malfunctioning devices will be returned to the Sponsor by the Site for further evaluation.

In case of subject death, it is requested that a copy of the death certificate and a copy of the autopsy report, if applicable, be sent to the CRO. Any other source documents related to the death should also be provided to the CRO. If no source documents are available, the PI is required to describe the circumstances of the subject's death in written communication (e.g., letter, e-mail).

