7.2 Secondary Endpoints

The secondary endpoints for the study are:

- Frequency of successful recanalization (defined as angiographic confirmation of crossing the chronic total occlusion and restoring blood flow to the affected area).
- Frequency of MACE through discharge or 24 hours post-procedure, whichever comes first (in-hospital), and at 30 days post-procedure (see **section 14.0** for MACE definition). The components of MACE will also be reported separately.
- Frequency of clinically significant perforation (defined as any perforation resulting in hemodynamic instability and/or requiring intervention including pericardiocentesis, embolization, prolonged balloon occlusion, stent graft, or comparable therapy).
- Procedural success according to crossing technique.
- Technical success (see **section 14.0** for definition).

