9.4 Point of Enrollment & Numbering of Study Subjects

A patient will be considered enrolled as a study subject once an investigational guidewire has entered the guide catheter.

The site staff assigns the lowest available subject number progressing sequentially for each enrolled subject (e.g., 001, 002, 003). As soon as possible after a subject is enrolled, a member of the site's study team will notify the CRO, preferably by an entry in the database (EDC) or via email notification.

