9.6.2 Pre-PCI Procedure Angiogram

Selection criteria for access approach (femoral or radial artery) will be at the discretion of the Investigator and will be based on a variety of clinical factors such as patient anatomy, vasculature, and other possible comorbidities.

Standard catheterization and angiographic procedures will be followed during this study and any adverse events that occur during and after the procedure will be collected. A pre-procedure angiogram of the target vessel will be completed per the Angiographic Core Laboratory Guidelines prior to any interventions on the CTO. Assessment of angiographic eligibility is based on a visual assessment of the pre-procedure angiogram.

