9.6.3 PCI Procedure

The PCI procedure will be performed with the study device(s) following these guidelines:

- At least one Teleflex guidewire and at least one Turnpike catheter must be used during a study PCI procedure
- The R350 guidewire should be used for all retrograde cases for which wire externalization is performed.
- The GuideLiner catheter or TrapLiner catheter should be used when any guide extension is necessary for completion of a study PCI procedure
- Additional study devices and commercially available guidewires and catheters may be used during a study PCI procedure at the discretion of the physician

Post-procedure angiographic imaging of the CTO must be captured and performed per the instructions provided by the core laboratory and must be captured in a precise manner as was used for the pre-procedure images. Angiographic images of the CTO must be sent to the core lab per specified method.

If the subject is returned to the procedure room and a guiding catheter is reinserted and a dilatation is performed, this will be considered a repeat intervention.

Standard PCI procedural data will be collected on the CRFs such as:

- Vessel and lesion characteristics
- TIMI grade flow pre and post treatment
- Approach technique(s)
- Type and size of devices used
- The order in which guidewires were used and which guidewire was the crossing guidewire
- Procedural durations including start/end times
- Air Kerma (Gy) and total fluoroscopy time
- Procedure-related medications
- Adverse event assessment including perforation and dissection classifications
- Device deficiency assessment

See **Section 14.0** for procedure-related definitions and **Table 5** below for recommendations for procedure-related medications.

Table 5: Procedure-Related Medications Recommendations

Timepoint	Medication Recommendations
Pre-procedure	
Aspirin: 100-325 mg non-enteric coated aspirin orally at least one hour and no more than 23 hours prior to procedure, or per hospital protocol.Clopidogrel: 300 mg loading dose the day before the procedure or 600 mg the day of the procedure or sufficient existing steady state blood concentration, or per hospital protocol. If the patient had been taking Clopidogrel (75 mg/day) for three or more consecutive days prior to the procedure, the loading dose need not be given. 
Note: The use of glycoprotein IIb/IIIa inhibitors is not recommended.

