Procedure times [*aligns with Asahi Intecc CTO-PCI, NCT02379923; ref. Kandzari 2018*]:

- **Procedure start time:** The first successful insertion of the guide catheter at an arteriotomy site is considered the start of the procedure.
- **Procedure end time:** The procedure is considered complete once the guide catheter is removed from the arteriotomy site.
- **Total study device procedure time:** The first successful insertion of a study device (catheter or guidewire) into the target artery is considered the start of the study device procedure. The study device procedure is considered complete once all study devices have been removed.

Serious adverse event (SAE): Any untoward medical occurrence that results in death, is life-threatening, requires inpatient hospitalization or prolongation of existing hospitalization, or results in persistent or significant disability/incapacity. [*ref: ICH E6(R2) Good Clinical Practice: Consolidated Guidance*]

- Note: An AE is considered “life-threatening” if, in the view of either the Investigator or Sponsor, its occurrence places the subject at immediate risk of death. It does not include an AE that, had it occurred in a more severe form, might have caused death.

Successful recanalization: Angiographic confirmation of crossing the chronic total occlusion and restoring blood flow to the affected area. [*aligns with Asahi Intecc CTO-PCI, NCT02379923; ref. Kandzari 2018*]

Target lesion: The CTO lesion being treated.

Technical success: Successful guidewire recanalization. [Kandzari 2018]

- Note: The technical success definition is applicable to investigational devices as at least one investigational guidewire must be used in every procedure.

TIMI: Thrombolysis in myocardial infarction grading scale. [TIMI Study Group, 1985]

TIMI 0 - no perfusion	There is no antegrade flow beyond the point of occlusion.
TIMI I - penetration without perfusion	The contrast material passes beyond the area of obstruction but “hangs up” and fails to opacify the entire coronary bed distal to the obstruction for the duration of the cineangiographic filming sequence.

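### Protocol sections 11.2 and 9.6.2 give different start points for adverse event collection, so harm from a study catheter before the first study guidewire may or may not be counted

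*Protocol*

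**What the plan says.** Protocol 11.2, the section on collecting and documenting adverse events, sets the start: "Collection of adverse events will start when subjects are enrolled and will be assessed and reported throughout the study". Protocol 9.4 says when that is: "A patient will be considered enrolled as a study subject once an investigational guidewire has entered the guide catheter".

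Protocol 9.6.2 has no enrolment condition: "any adverse events that occur during and after the procedure will be collected". Table 4 likewise lists adverse event monitoring under the PCI procedure. Protocol 14.0 dates the procedure from an earlier moment: "The first successful insertion of the guide catheter at an arteriotomy site is considered the start of the procedure".

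Two further provisions bear on what can happen in between. Protocol 9.6.3 states: "Additional study devices and commercially available guidewires and catheters may be used during a study PCI procedure at the discretion of the physician". Protocol 14.0, defining study device time, allows a catheter to go in first: "The first successful insertion of a study device (catheter or guidewire) into the target artery is considered the start of the study device procedure".

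SAP 9.4 describes the adverse event summaries but gives no start time for collection.

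**The concern.** The two rules differ by the interval between guide catheter insertion and entry of the first study guidewire. Work on the occlusion can take place in that interval, and it can involve devices under study. A Turnpike is required in every case, yet neither a Turnpike nor a guide extension catheter triggers enrolment.

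Take a subject whose vessel is injured by a Turnpike advanced over a commercial wire, and in whom a study guidewire is used a few minutes later. The subject is enrolled and analysed. A coordinator following 11.2 could properly leave the injury off the Adverse Event form, because it came before collection began. A coordinator following 9.6.2 would record it. The difference runs one way: the 11.2 reading can drop events but cannot add any. In a single-arm study no control group is under-counted to the same degree.

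**Working it through.** The documents state no rate of harm before the first study guidewire, so the check is mainly a comparison of text.

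**1. Order of events within one procedure**

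| Moment | Source | Collecting under 9.6.2 and Table 4? | Collecting under 11.2? |
|---|---|---|---|
| Guide catheter inserted | Protocol 14.0, procedure start | Yes | No |
| Commercial wire, or study catheter over it | Protocol 9.6.3 and 14.0 | Yes | No |
| Study guidewire enters guide catheter | Protocol 9.4, enrolment | Yes | Yes |
| Guide catheter removed, then follow-up | Protocol 14.0 and Table 4 | Yes | Yes |

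**2. Is the second row permitted?** Yes. Section 9.6.3 requires at least one study guidewire and one Turnpike but sets no order. It has the order of guidewires recorded, so varying sequences are expected. Table 2 describes the Turnpike as delivered over a guidewire, without requiring a study wire.

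**3. Does the SAP settle it?** No. SAP 9.4 sets no start, and SAP 8.3 counts study days from calendar dates, so it cannot separate two moments within one procedure.

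**4. Which outputs can change?**
- *Adverse event tables, including by relatedness:* yes. They rest on what sites report on the Adverse Event form.
- *Clinically significant perforation:* possibly. The endpoint is worded without a start time: "Frequency of clinically significant perforation (defined as any perforation resulting in hemodynamic instability and/or requiring intervention". The procedural data in 9.6.3 include "Adverse event assessment including perforation and dissection classifications". A perforation may therefore be captured whatever 11.2 says.
- *MACE and the primary endpoint:* essentially not. A subject who is later enrolled was alive when the study guidewire went in, so cardiac death cannot precede enrolment. MI is defined as post-procedural, with CK-MB drawn at 6–12 hours and at 18–24 hours or discharge. Target lesion revascularisation would ordinarily follow the index treatment. A perforation without MACE does not enter the primary endpoint.
- *Sample size:* not. With p0 = 0.632, p1 = 0.732 and one-sided alpha 0.05, the first N from 100 upward with exact binomial power of at least 80% is 135 (success at 95 or more; alpha 0.0491, power 0.8006). This matches Protocol 7.3.6 and SAP 11. No input depends on when adverse event collection starts.

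**5. Size of the loss.** Let r be the true rate of an in-procedure complication and q the share occurring before the first study guidewire. If every site follows 11.2 literally and no other form captures the event, the reported rate is r × (1 − q). Neither r nor q is in the documents. As pure illustration, assume r = 6% (0.06 × 150 = 9 events) and q from 10% to 30%:
- q = 10%: 6% × 0.9 = 5.4%; expected loss 9 × 0.1 = 0.9 events
- q = 30%: 6% × 0.7 = 4.2%; expected loss 9 × 0.3 = 2.7 events

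The loss scales with the assumed r. For given r and q these figures are ceilings, because 9.6.2 and the procedure form will lead some sites to record such events.

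**The case against.** The two sections can be read together: 11.2 says whose events are collected (enrolled subjects) and 9.6.2 says which of their events count (those during and after the procedure). Nothing makes 11.2 prevail over 9.6.2. Table 4 and the perforation and dissection items among the procedural data favour the wider reading, and the device-deficiency paragraph of 11.2 carries no enrolment trigger. The affected outputs are descriptive. A clinically significant perforation before the first study guidewire, followed by insertion of that guidewire, also needs a particular chain of events. If the operator stops instead, the patient is never enrolled, which is a separate matter.

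Most of this stands, and it keeps the point minor. It does not remove the conflict. The 11.2 sentence is about when collection starts, and the harmonised reading is not written down. An endpoint definition counts only events that reach the database, and Protocol 11.4 likewise speaks of reported MACE. Full source monitoring under Protocol 13.6 need not recover an omitted event, because a site following 11.2 has not deviated.

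A reader might go further and infer that all harm before the study guidewire falls outside the safety endpoints. The documents do not support that: 9.6.2 says the opposite, and the perforation and MACE definitions contain no enrolment start.

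**Conclusion.** The conflict holds. Sections 11.2 and 9.6.2 set different start points for the same data, and nothing in the protocol or SAP chooses between them. In subjects who are later enrolled, harm in the interval, including harm from study catheters, may be reported at one site and not at another. Any error is an under-count. The reach is limited to the adverse event and relatedness tables and possibly the clinically significant perforation count, none of which carries a hypothesis test. The size cannot be derived from the documents; the illustration rests on an assumed 6% rate and an assumed early share of 10% to 30%.

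A reader might also infer that the test against the 63.2% goal is made easier to pass. That would require primary-endpoint failures to go uncounted, and for subjects who go on to be enrolled the MACE components leave essentially no route for it. Severity: minor.

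**What to change.** In Protocol 11.2, replace the enrolment start with: *at the procedure start time (section 14.0) for every subject who is enrolled*. This uses an existing definition and brings 11.2 into line with 9.6.2 and Table 4. Apply the same start to the perforation, dissection and device-deficiency records. Add one field to the Adverse Event form for whether onset was before or after the first study guidewire entered the guide catheter, so that both counts can be shown.

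The cost is one sentence and one form field. The downside is a possibly slightly higher reported complication rate that includes some events due to commercial devices. The CEC's relatedness classification, already planned, can separate these.

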11.3 Adverse Event Reporting Timeframes

The Investigator is responsible for reporting serious adverse events to the IRB in accordance with the IRB's procedures. Unanticipated adverse device effects (UADEs) have special reporting requirements for both the Investigator and Sponsor, as described in 21CFR812.150:

- **Investigator Report:** If a subject experiences a UADE, the Investigator must notify the Sponsor and the reviewing IRB as soon as possible, but no later than 10 working days after the Investigator first learns of the effect.
- **Sponsor Report:** UADEs will be reported to the Food and Drug Administration (FDA), all reviewing IRBs, and participating Investigators as soon as possible, but no later than 10 working days after receiving notice of the UADE.

Sites will also follow regulations for reporting serious device-related injury and/or deaths by way of the MedWatch process (Medical Device Reporting [MDR] for Device User Facilities for FDA approved/cleared product). The FDA and Sponsor understand that FDA may receive duplicate reports of serious potentially related adverse events due to the clinical trial data collection process and the duplicate MDR reporting process. The FDA and Sponsor also understand that event information may be reported via the MDR process prior to Sponsor event monitoring and CEC adjudication.

11.4 Adverse Event Relationship

The Investigator and the CEC will assess the relationship of the adverse event to the device treatment or procedure as follows:

- **Definitely:** The adverse event follows a strong temporal sequence to the receipt (or attempted receipt) of the device treatment or procedure. This can include an adverse event that occurs after the study procedure.
- **Probably:** The adverse event follows a reasonable temporal sequence to the receipt (or attempted receipt) of the device treatment or procedure, and the possibilities of other factors, such as underlying and concomitant illness, concomitant medications, or concurrent treatment can be excluded.
- **Possibly:** The adverse event follows a reasonable temporal sequence from receipt (or attempted receipt) of the device treatment or procedure and the possibility of device

treatment or procedure involvement cannot be excluded. However, other factors such as underlying or concomitant illness, concomitant medications, or concurrent treatment are presumable.

- **Unlikely:** The adverse event has an improbable temporal sequence to the receipt (or attempted receipt) of the device treatment or procedure, or it can be reasonably explained by other factors, including underlying or concomitant illness, concomitant medications, or concurrent treatment.
- **Not Related:** The adverse event has no temporal sequence to the interventional procedure, the device treatment, or any user handling, or it can be explained by other factors, including underlying disease or concomitant illness, concomitant medication, or concurrent treatment.

Adverse events adjudicated by the CEC as *definitely* or *probably* will be considered related adverse events for data analytic purposes. Events adjudicated by the CEC as *possibly*, *unlikely* or *not related* will not be considered related adverse events for data analytic purposes.

All reported major cardiac adverse events, regardless of relationship, will result in a procedure failure for data analytic purposes. Refer to **Section 14.0** for definitions of MACE and procedure success.

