7.3.5 Safety Analysis

Summary tables and listings will be provided for all reported adverse events, which will additionally be reported by seriousness and relatedness. Such summaries will be comprised of the number and percentage of subjects with an adverse event and the total number of such events. The proportion of subjects with events will be considered primary for analysis of adverse events.

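### Events graded possibly related are left out of the related-event rate, and the causality classes overlap across that cut, so the rate should be shown both ways and the classes made exclusive

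*Protocol*

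**What the plan says.** Protocol 11.4 defines five levels of relationship to the device treatment or procedure. CEC grades of *definitely* or *probably* "will be considered related adverse events for data analytic purposes". The other three, *possibly*, *unlikely* and *not related*, "will not be considered related adverse events for data analytic purposes".

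The definitions that matter here are these:

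- *Definitely*: "The adverse event follows a strong temporal sequence to the receipt (or attempted receipt) of the device treatment or procedure". Nothing is said about other causes.
- *Probably*: reasonable timing, and other factors such as illness, medication "or concurrent treatment can be excluded".
- *Possibly*: reasonable timing, other factors presumed, and "treatment or procedure involvement cannot be excluded".
- *Unlikely*: improbable timing, "or it can be reasonably explained by other factors, including underlying or concomitant illness". *Not related* has the same two-branch structure, with no temporal sequence as its first branch.

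Protocol 7.3.5 promises tables and listings of all adverse events, "which will additionally be reported by seriousness and relatedness", and makes the proportion of subjects with events the main measure. SAP 9.4 has the CEC classify relationship but does not restate the cut, and it plans no second tabulation. Protocol 10.1 refers to written CEC guidelines, which are not part of the documents.

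**The concern.** There are two separate problems. First, the protocol describes *possibly* as a grade at which a link cannot be ruled out, and then analyses it on the same side as events judged unrelated. Second, the top grade is less demanding about other causes than the grade below it, so one event can meet the wording of a class that counts as related and of classes that do not.

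What is at stake is a reported safety result in a single-arm study meant to support 510(k) clearance. With no concurrent control, a reader cannot tell from the planned summaries whether a low related-event rate reflects the devices or the counting rule. *Possibly* may also be well populated. Subjects have ischaemic heart disease, antithrombotic drugs are recommended around the procedure, and other commercial wires and catheters may be used in the same case (Protocol 9.6.3), so the exclusion that *probably* demands will often be hard to make. That is an inference; the documents give no expected split.

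**Working it through.** **Does the point touch a design figure?** The documents state no related-event rate, threshold or hypothesis. The one figure that can be reproduced is the evaluable sample size of 135 (Protocol 7.3.6; SAP 11). An exact one-sided binomial test of 63.2% against 73.2% at alpha 0.05 with n = 135 rejects at 95 or more successes, with exact alpha 0.0491 and power 0.8006. So 135 is reproduced. It does not change, because relatedness does not enter the primary endpoint: Protocol 11.4 makes any MACE a procedure failure whatever its relationship.

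**The cut.** Let D be the number of subjects with at least one *definitely* or *probably* event, P the number whose only candidate event is *possibly*, and N the number of subjects.

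- Rate under the plan: D / N
- Rate including *possibly*: (D + P) / N
- Difference: P / N, which is never negative

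Each subject in P adds 1/150 = 0.67 points at N = 150, or 1/135 = 0.74 points at N = 135. Neither D nor P is given, so the difference itself cannot be derived. To show the scale only, assume D = 6 and N = 150 (exact 95% intervals):

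| P (assumed) | Rate including *possibly* | 95% interval |
|---|---|---|
| 0 | 6/150 = 4.0% | 1.5% to 8.5% |
| 3 | 9/150 = 6.0% | 2.8% to 11.1% |
| 6 | 12/150 = 8.0% | 4.2% to 13.6% |
| 15 | 21/150 = 14.0% | 8.9% to 20.6% |

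The plan would report 4.0% in every row.

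**The overlap.** Take an event soon after the procedure that another illness could also explain, and read it against each definition:

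| Class | Timing required | Other causes | Does the event fit? | Analysed as |
|---|---|---|---|---|
| *Definitely* | strong | not mentioned | yes | related |
| *Probably* | reasonable | must be excluded | no | related |
| *Possibly* | reasonable | presumed; involvement not excluded | yes | not related |
| *Unlikely* | any, through its second branch | reasonably explain the event | yes | not related |
| *Not related* | any, through its second branch | explain the event | yes | not related |

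The event fits four classes, one counted and three not. Overlap among the last three does not alter the planned rate, because all three fall on the same side of the cut. *Probably* does not overlap with them, since it requires other causes to be excluded. The overlap that crosses the cut therefore comes from *definitely*.

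Its direction is open. If timing decides, such events are counted and the rate rises. If the alternative explanation decides, they are not counted and the rate falls. The documents contain no rule for choosing.

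**The case against.** The case on the other side has real force. The cut is explicit, prespecified and applied to the grades of a committee that includes no study investigators. No section defines related as covering every event whose link cannot be ruled out, so preferring a wider definition is a choice and not the correction of an error. Containment is good: MACE counts as failure regardless of relationship, the MACE and perforation endpoints carry no relatedness filter, the overall proportion of subjects with events is reported, and SAP 9.4 promises listings of all adverse events. The unseen CEC guidelines may hold a precedence rule.

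Most of this stands, and it limits the point to a descriptive breakdown. It does not remove the point. Being prespecified does not show a reader how far the result depends on the cut, and guidelines outside the protocol do not repair definitions in the protocol that conflict with each other.

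A reader might go further and infer that the cut and the overlap together bias the related-event rate low. The documents do not support that. The overlap has no known sign, because a timing-only *definitely* can also draw in events with another cause. For the cut, low holds only relative to a definition that includes *possibly*.

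**Conclusion.** The point holds in a limited form, and the change should be made. Relative to a definition that includes *possibly*, the planned related-event rate is lower or equal, by P/N; that is 0.67 points per additional subject at 150, with a total the documents do not determine. The illustrative rates above rest on assumed counts and predict nothing about this study. Separately, the wording lets an event fall on either side of the cut, so classification is unreliable in an unknown direction. This rests on reading the definitions as written and on no precedence rule existing elsewhere. Nothing here changes the primary endpoint, the sample size, the MACE and perforation endpoints, the overall adverse event rate or the listings.

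**What to change.** 1. In Protocol 11.4 and SAP 9.4, keep the prespecified cut, state it in the SAP, and tabulate beside it the proportion of subjects with related events when *possibly* is included.
2. In Protocol 11.4, make *definitely* at least as strict as *probably* by also requiring that other causes are excluded, or add a precedence rule so that each event fits one class. The precedence rule is the more complete choice: the second column puts a boundary between *possibly* and the two grades below it, where overlap that is harmless under the present cut would begin to matter.

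The cost is one table column, a wording change and a second figure that will be equal or less favourable. No new data are needed, since the five grades are already assigned. Tightening *definitely* may lower the figure under the existing cut, because early events with another cause would leave it.
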